6.5 Early Withdrawal of Subjects

Participants will be removed from the protocol if:

- 1) Study imaging is not completed for any reason. The subject withdraws consent.
- 2) The subject has an occurrence of a significant clinical event that precludes imaging.
- 3) The subject becomes pregnant.

If a participant is withdrawn from the protocol, the PI will mark the data of this subject as "withdrawn" and will add a detailed explanation about the cause of withdrawal in the database.

6.6 Study drug and device

6.6a Description

This study is neither a drug nor a device trial. Patients will be administered FDA approved ICG through intravenous injection and imaged by a FDA approved surgical microscope (Pentero,SPY Elite, or SPY PHI) which is 0.5 meter away from the subject. Both ICG fluorescence and the two imaging systems have been used for routine clinical practice for many years. Figure (a) shows the Schematic sketch of the imaging systems. ICG fluorescence imaging utilizes intravenously injected ICG, which is a fluorescent dye that is FDA-approved for clinical use, illuminated with near-infrared light. The ICG dye is indirectly activated and the dynamic fluorescence due to bone perfusion can be captured by a video rate imaging system.

6.6.b Preparation and Administration of Study Drug

ICG used in this study is purchased from Novodag/Stryker.

6.6.c ICG Preparation and Administration Procedures:

- 1) ICG is prepared by the Surgical and/or Anesthesia teams in the operating room on the day of surgery.
- 2) From the vial containing ICG, the required dose is withdrawn into a syringe, labeled, and administered through a peripheral intravenous line followed by a saline flush.

6.7 Study Procedures

On the surgery day, the patient will be prepared and transported to surgery as per routine at Dartmouth-Hitchcock. In the OR, patient positioning, preparation of the surgical field, and draping will follow standard practice.

Prior to ICG administration, patients will undergo standard preoperative monitoring by the Same Day nursing staff that includes continuous pulse oximetry, blood pressure monitoring, and heart rate, and respiratory rate. These results will be available prior to surgery and prior to administration of ICG. ICG will be administered by an anesthetist in the operating room. Patients are under the care and observation of the anesthesia and surgical teams during this time. Postoperatively, patients are transferred to the Post-Anesthesia Care Unit (PACU) where they are monitored continuously by nursing staff supervised by anesthesiologists. During this entire time vital signs (including temperature, pulse, respiratory rate and blood pressure) are collected as standard of care. All clinical data will be reviewed for adverse events for a period of 30 minutes post-injection.

Day of surgery Procedures	Pre- Infusion	0-30 minutes post- infusion
Pulse	X	X
Blood Pressure	X	X
Temperature	X	X
Respiratory Rate	X	X
Adverse Events		X

A Pulse dye densometer (Pulsion Medical Systems), similar to a pulse oximetry probe, will be placed on the patient's finger to acquire an arterial blood input function during ICG injection. After exposure of the tibia or femur 0.1 mg/kg ICG will be injected intravenously. Video rate ICG fluorescence images will be acquired 20 seconds before and 4 minutes after ICG injection. Osteotomy or bone cut will be performed and then 0.1 mg/kg ICG will be injected intravenously and, again, video rate ICG fluorescence images will be acquired 20 seconds before and 4 minutes after ICG injection. Soft tissue stripping from tibia or femur will then be performed, per standard surgical procedure. Then a third dose of 0.1mg/kg ICG will be injected and video rate ICG fluorescence images will be acquired 20 seconds before and 4 minutes after ICG injection. There will be a minimum of 5 minutes between ICG infusions to allow ICG to wash out of tissues.

Surgical plan will not be affected as a result of the intraoperative fluorescence imaging. Surgical care team will be blinded to the imaging results in the operating room. The

imaging screen will be either be covered or hidden from view of the surgical team. The operator of the imagine device may visualize the imaging screen to ensure integrity of imaging data collection but this person will not communicate the results to the surgical team.

There is no follow-up associated with this study.

7.0 Data and Specimen Banking*

Not applicable

8.0 Sharing of Results with Subjects*

This study is not intended to provide any results to the subjects because this is the investigational study and the subjects will be under standard practice for their condition and no diagnostic or therapeutic decisions will occur based on the study.

9.0 Study Timelines*

This study is a one-time imaging during the subject's surgery. The duration of each subject enrolled in the study is from the date the subject signs the consent to the day that the surgery is carried out.

The duration to enroll all study subjects is Jan.2, 2020 – Dec.31, 2021.

The estimated date for the investigators to complete this study is Jan. 31, 2022

10.0 Inclusion and Exclusion Criteria*

Inclusion Criteria

- a. Patients 18 years of age or older
- b. Scheduled for a lower extremity amputation (either below knee, through knee or above knee)
- c. Provision of informed consent

Exclusion Criteria

- a. Iodine allergy
- b. Pregnant women
- c. Patients under the age of 18.
- d. Prisoners
- e. Pregnant of nursing mothers

Vulnerable Populations*

After the consent has been reviewed with a potential subject, the subject will be asked to tell the research team member two things about the research they recall. If they are not able to do so the subject will be considered incompetent to consent to the research trial. Patients found to be in capable of providing informed consent will be deemed by the research staff to have impaired decision making and therefore will only be consented if a LAR agrees to their participation and signs the consent form.

Patients with impaired decision-making capacity will be included in this study. If the patient is unable to provide informed consent (e.g. due to their injury) at the time they are identified, informed consent may be obtained from their legally authorized representative (LAR). Allowing informed consent from a patient's LAR will reduce the risk of recruitment bias against the most severely infected patients.

For patient with impaired decision-making capacity, a LAR with knowledge of the potential participant will be approached to consent on the patient's behalf. If the patient cannot adequately answer at least two questions and it is determined that the patient's level of cognition is not likely to change before surgery, their LAR will be approached. The choice of LAR will follow standard procedures. The following will be approached in this order of priority:

- legal guardian
- proxy (health care agent) named in an advanced directive or durable power of attorney for health-care

The LAR will be advised to base the decision on the participant's expressed wishes, or, if these are not known, what they believe the participant would have desired under the circumstances of the injury, their beliefs and values. Recognizing that consent is an ongoing process, the study team will encourage the participants to ask additional questions that may arise during the course of their participation in the study.

Subjects participation in this study completely voluntary. If at any time a patient finds participation to be unduly stressful the patient or their legal authorized representative may withdraw the patient from the study with no repercussions.

Assent will be obtained from all patients that are able to sign their name. If patients are injured so severely that they are not able to sign their name verbal assent will be obtained. Assent will not be obtained from patients whom are unconscious due to the nature of their injury.

The study team will comply with consent procedures for cognitively impaired adults outlined in SOP HRP-013.

11.0 Local Number of Subjects

The primary outcome measure is total bone blood flow (TBBF). Informed by data collected from the porcine study, a total sample size of 30 trans-tibial amputation patients is required to determine the difference in TBBF baseline bone perfusion kinetics and change in the bone perfusion kinetics associated with osteotomy and subsequent soft tissue stripping. Considering that the controlled environment associate with the porcine model may not be replicated to the same degree in the amputation sample, a more conservative difference of 0.84 standard deviations between baseline and osteotomy and soft tissue stripping was selected (i.e., 50% of the effect size identified in the porcine model). Assuming a one tailed test, a Type I error rate of 0.05, and a Type II error rate of 0.80, a sample of 20 was determined with an additional 10 amputation patients recruited in the event that there is any protocol- or data-related issues. Data analysis will be performed after half of the patients are enrolled to re-calculate sample size needed to determine a difference.

We anticipate that 20 subjects will be accrued locally. We anticipate that 20 patients will be enrolled at Brigham and Women's Hospital. A total of 40 patients will be enrolled.

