25.0 Multi-Site Research*

This study will be conducted at two clinical sites,

- Dartmouth-Hitchcock Medical Center
- Brigham and Women's Hospital

We anticipate that 20 subjects will be accrued locally. We anticipate that 20 patients will be enrolled at Brigham and Women's Hospital. A total of 40 patients will be enrolled.

This distribution of patients is subject to change during monitoring of rate enrollment at each clinical site.

All data will be communicated in a HIPPA-compliant manner using a HIPPA-compliant database for clinical data (REDCap) and a HIPPA-compliant storage drive for imaging data. Clinical and imaging data will be uploaded to the appropriate HIPPA-compliant site by the local research team at each institution and all data will be analyzed at either Dartmouth-Hitchcock Medical Center or Dartmouth College/Thayer School of Engineering. De-identified patient information using a Study ID number will be utilized when possible.

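### Section 11.0 requires a total of 30 patients and then enrols a total of 40, so the half-way sample-size re-calculation falls at 15 or 20; its trans-tibial wording also disagrees with the eligibility criteria.

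*Protocol*

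**What the plan says.** All references are to the Protocol.

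- **Total of 30.** Section 1.0 gives a sample size of 30. The first paragraph of Section 11.0 states that "a total sample size of 30 trans-tibial amputation patients is required" and shows how it is built: "a sample of 20 was determined with an additional 10 amputation patients recruited", the extra 10 being held "in the event that there is any protocol- or data-related issues".
- **Total of 40.** The second paragraph of Section 11.0 expects 20 patients locally and 20 at the second site, and concludes: "A total of 40 patients will be enrolled". Section 25.0 repeats it: "We anticipate that 20 patients will be enrolled at Brigham and Women's Hospital. A total of 40 patients will be enrolled".
- **Stated flexibility.** Section 25.0 adds: "This distribution of patients is subject to change during monitoring of rate enrollment at each clinical site".
- **Re-calculation.** Section 11.0: "Data analysis will be performed after half of the patients are enrolled to re-calculate sample size needed to determine a difference".
- **Effect size.** Section 11.0: "a more conservative difference of 0.84 standard deviations between baseline and osteotomy and soft tissue stripping was selected", with a one-tailed test at 0.05. A value of 0.80 is printed as the Type II error rate.
- **Population.** Sections 6.1, 6.2, 10.0 and 12.0 admit below-knee, through-knee and above-knee amputation. Section 6.7 describes imaging of the tibia or the femur.

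**The concern.** The two totals cannot both be followed. Stopping at 30 agrees with Section 1.0 and the first paragraph of Section 11.0, but not with the second paragraph or Section 25.0. Going on to 40 adds 10 patients beyond a requirement that already contains its reserve, and no reason is given. Under Section 14.0 each patient receives three ICG injections, so the difference is 10 × 3 = 30 injections, in patients who by Section 15.0 gain no direct benefit.

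Two things follow from, or sit beside, the conflict. The re-calculation is set at half of a total that is not settled, so its timing is not settled either. And the calculation is worded for trans-tibial patients, while the trial recruits a wider group. If the calculated 20 is meant to be trans-tibial, nothing in the Protocol ensures that 20 such patients are enrolled. If it is not, the word is wrong.

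**Working it through.** **1. The totals.** First paragraph of Section 11.0: 20 + 10 = 30. Second paragraph: 20 + 20 = 40. The difference is 10 patients, or 10/30 = 33% above the stated requirement. The reserve above the calculated 20 is 10 of 30 (33%) or 20 of 40 (50%). Only the first reserve is explained.

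**2. Can the two be reconciled?** Three routes were tried.
- *Local versus overall.* The heading of Section 11.0 refers to local numbers, but 30 is called a total and the local figure is 20.
- *Flexible enrolment.* The sentence in Section 25.0 covers the split between sites, not the sum.
- *Result of the re-calculation.* The 40 is stated as the plan, not as an outcome of that later analysis.

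None explains the step from 30 to 40.

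**3. The re-calculation point.** Half of 30 is 15; half of 40 is 20.

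**4. Does the calculated 20 reproduce?** Inputs from Section 11.0: d = 0.84, one-sided alpha 0.05. The 0.80 is read as power (assumption); taken literally as Type II error it would give about 3 patients.
- Two-sample, normal approximation: n per group = 2 × (1.645 + 0.842)² / 0.84² = 17.5, so 18; by the noncentral t, 19.
- Paired, 0.84 in SDs of raw values, zero within-patient correlation (assumption): d becomes 0.84/√2 = 0.594, and n = 19 by the noncentral t.
- Paired, 0.84 in SDs of the within-patient change: (1.645 + 0.842)² / 0.84² = 8.8, so 9; by the noncentral t, 11.

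The stated 20 is therefore close to the first two readings. The Protocol does not say which SD is meant.

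**5. Power at each number** (noncentral t, one-sided 0.05; noncentrality 0.84√n for the change, 0.84√(n/2) for the other two):

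| Reading of 0.84 SD | n = 20 | n = 30 | n = 40 |
|---|---|---|---|
| SD of within-patient change | 0.976 | 0.998 | >0.999 |
| Two-sample, n per group | 0.832 | 0.942 | 0.981 |
| Paired, zero correlation | 0.820 | 0.937 | 0.980 |

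The lowest entry is 0.82.

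**6. Does 15 versus 20 matter for the re-calculation?** The 95% interval for an SD, as a multiple of its estimate (chi-square), is 0.73 to 1.58 at 15 and 0.76 to 1.46 at 20. Both are wide, and 20 is somewhat more precise.

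**7. Trans-tibial share.** If the 20 must all be trans-tibial, 20/30 = 67% of a total of 30 or 20/40 = 50% of a total of 40 would have to be. The Protocol states no expected share and no quota.

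**The case against.** The strongest reply is that little is at stake. Power is adequate at either total, the study is described in Section 3.0 as gathering pilot data, a re-calculation is planned so the total is provisional, and Section 14.0 calls the risks minimal. With its severe reaction rate of 0.05%, taken per patient, ten more patients carry 10 × 0.0005 = 0.005 expected events. This stands as a limit on the harm. It does not remove the contradiction: even a provisional total needs one starting value, and an analysis plan cannot settle which of two protocol enrolment totals applies.

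Several stronger readings are tempting, and the document does not support them.
- *The trial is underpowered.* It is not on its own inputs; both totals exceed the calculated 20.
- *The re-calculation could fall at 10.* That halves the calculated 20, which is never the enrolment total. The supported choices are 15 and 20.
- *The re-calculation must come before patient 20.* Nothing requires this. At 20 of 40, half of enrolment is still to come, and an earlier look estimates the SD less precisely.
- *The enrolled population is not fixed.* Eligibility agrees across four sections. Trans-tibial appears once, and the rest of that paragraph speaks of amputation patients without a level. The fault is a mismatch in the sample-size statement.
- *The 40 supersedes the 30 because a second site was added.* This may be the history, but the Protocol does not say so.

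**Conclusion.** The contradiction holds and should be fixed. The current text gives two totals, 30 and 40, that differ by 10 patients with no stated reason. As a direct result the re-calculation point is 15 or 20. The trans-tibial wording is a smaller, separate mismatch with consistent eligibility criteria; its importance depends on whether the 20 was meant to count trans-tibial patients only, which the Protocol does not establish.

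The finding on the totals needs no assumption beyond the text. The statement that power is not at issue assumes that 0.80 means power and that 0.84 SD holds in the patients enrolled; on that basis power is at least about 80% at 20, 30 or 40 under the three readings checked.

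**What to change.** 1. State one total in Sections 1.0, 11.0 and 25.0, derived in Section 11.0 as calculated number plus reserve: 20 + 10 = 30, or 20 + 20 = 40 with a reason for the larger reserve. Make the expected numbers per site add up to it.
2. Replace the reference to half of the patients by the matching number: 15 if the total is 30, 20 if it is 40. Either is workable.
3. Reconcile the trans-tibial wording with eligibility in one of two ways: name all three amputation levels and say why 0.84 SD applies to them, or state that the calculated 20 counts trans-tibial patients only and count enrolment by level.

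**Cost.** Protocol wording only, plus a running count by level under the trans-tibial option. Under the all-levels option the justification of 0.84 SD needs some care: 20 patients keep 80% power down to 0.58 SD if the figure refers to the within-patient change, but only to about 0.80 SD on the two-sample reading, which leaves almost no margin before the reserve is counted.

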14.0 Risks to Subjects*

Risk of ICG injection: ICG (Indocyanine Green) will be administered intravenously three times: once after exposure, once after osteotomy and once after soft tissue stripping. ICG is FDA approved for human use in angiography for ophthalmology and cardiology applications and is given routinely to patients in these clinical settings. The risks are considered minimal and consist of nausea, vomiting, hives, increased heart rate in subjects with particular sensitivity to the dye. ICG does contain sodium iodide and patients with a history of allergy to iodides will be excluded. Anaphylactic or urticardial reactions are rare but have been reported in patients both with and without a history of allergy to iodides. Anaphylactic deaths have been reported following IGG administration during cardiac catheterization. Reported rates of mild, moderate and severe adverse reactions to ICG are 0.15%, 0.2% and 0.05%. Every effort will be made to minimize this risk as much as possible. It is the standard of care at this institution to obtain information related to allergies, sensitivities and past medical histories upon patient arrival. Patients will also be monitored throughout their hospitalization, as is the standard of care, by everyone involved in their medical care for evidence of new or previously unknown reactions or sensitivities. Additionally, at all times ICG fluorescence imaging assessments are taking

place, research staff and both surgical and anesthesia staff will monitor patients closely for any adverse reaction to ICG. Research staff and surgical and anesthesia staff will also monitor patients for at least 30 minutes after all ICG fluorescence assessment procedures have been completed. In the event of an unexpected allergic reaction, Dartmouth-Hitchcock Medical Center and all affiliated groups within this institution have procedures in place for managing patients with unknown or unexpected allergic reactions. If such a reaction were to occur, all standard of care treatments will be provided including but not limited to treatment with appropriate agents such as epinephrine, antihistamines and corticosteroids. Risk of infection from IV injection is also extremely rare but can occur. Pregnant women are excluded from the study. A pregnancy test is administered to women of child-bearing age on request at no cost.

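### The sample-size paragraph gives a Type II error rate of 0.80 (20% power), which cannot produce its own sample of 20 and is the only power target on record for the mid-study re-calculation

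*Protocol*

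**What the plan says.** Protocol section 11.0 (Local Number of Subjects) contains the whole sample-size argument. The effect is set at half of that seen in the porcine work: "a more conservative difference of 0.84 standard deviations between baseline and osteotomy and soft tissue stripping was selected". The test is one-sided ("Assuming a one tailed test"). The error rates and the result follow: "Type I error rate of 0.05, and a Type II error rate of 0.80, a sample of 20 was determined". Ten more patients are added against protocol or data problems, which makes 30.

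The same paragraph then plans a data-driven step: "Data analysis will be performed after half of the patients are enrolled to re-calculate sample size needed to determine a difference". It gives no separate power target for that step.

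Section 14.0 (Risks to Subjects) confirms that each patient receives ICG "three times: once after exposure, once after osteotomy and once after soft tissue stripping", and section 6.7 describes imaging at each of these injections. The comparison with baseline is therefore within-patient. Section 11.0 does not say whether the 0.84 is in SDs of the within-patient difference or in SDs of the raw measurement. No other part of the protocol states a power or a Type II error rate.

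**The concern.** The Type II error rate is one minus the power. Read as written, the trial is designed to miss a true effect of the planned size four times in five. Nobody would plan that, and a sample of 20 at 0.84 SD does not correspond to it. Either the error rate or the sample must therefore be wrong.

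Two things are at stake. First, if the sample were the wrong one, the trial could be badly sized, so this has to be checked. Second, the re-calculation at half enrolment needs a power target and a defined SD to be reproducible, and the only error rate the protocol offers for it is 0.80.

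**Working it through.** **Inputs, all from section 11.0.** Standardised difference d = 0.84; one-sided test; α = 0.05; Type II error β = 0.80 as written; stated sample 20. The within-patient correlation ρ is not given, so 0, 0.3 and 0.5 are used below as assumptions.

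**Formulas.** Power comes from the noncentral t distribution: P(T > t₀.₉₅,df), with noncentrality nc.

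- Paired, 0.84 in SDs of the difference: dz = 0.84, nc = dz·√n, df = n − 1.
- Paired, 0.84 in raw SDs: dz = 0.84/√(2(1 − ρ)), with the same nc and df. This gives dz = 0.594 for ρ = 0, 0.710 for ρ = 0.3 and 0.84 for ρ = 0.5. The last case coincides with the difference-SD reading.
- Unpaired, n per group: nc = 0.84·√(n/2), df = 2n − 2.

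**Step 1: try to reproduce 20 with β = 0.80 (power 0.20).**

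- Difference SDs: power is 0.155 at n = 2 and 0.261 at n = 3, so n = 3.
- Raw SDs, ρ = 0: power is 0.239 at n = 4, the first n to reach 0.20, so n = 4.
- Unpaired: power is 0.217 at 3 per group, so 3 per group.

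The normal approximation asks for even fewer. For two samples, 2·((1.645 − 0.842)/0.84)² ≈ 1.8, which rounds up to 2 per group. No variant comes near 20.

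**Step 2: repeat with β = 0.20 (power 0.80).**

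- Unpaired: power is 0.815 at 19 per group, so 19 per group. The normal approximation gives 2·((1.645 + 0.842)/0.84)² ≈ 17.5, so 18.
- Raw SDs, ρ = 0: power is 0.801 at n = 19, so n = 19.
- Raw SDs, ρ = 0.3: n = 14.
- Difference SDs (or raw SDs with ρ = 0.5): power is 0.828 at n = 11, so n = 11.

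Two of these readings land within one of the stated 20. On the others, 20 is conservative.

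**Step 3: what 20 patients give, one-sided.**

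| Reading of 0.84 | n for 20% power | n for 80% power | Power at n = 20 | Type II error at n = 20 |
|---|---|---|---|---|
| Raw SDs, ρ = 0 | 4 | 19 | 82.0% | 0.18 |
| Raw SDs, ρ = 0.3 | 3 | 14 | 92.1% | 0.08 |
| Difference SDs, or raw SDs with ρ = 0.5 | 3 | 11 | 97.6% | 0.02 |
| Unpaired (n per group) | 3 | 19 | 83.2% | 0.17 |

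No row has a Type II error anywhere near 0.80.

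**The case against.** The strongest reply is that this is a slip of labelling with no effect on the trial. The intent is plain, 20 patients are enough for the stated test, and planned enrolment (30, or 40 later in the same section) exceeds 20 on any version. Anyone who entered 0.80 as the Type II rate at half enrolment would get 3 or 4 patients at the planning effect and notice at once. The protocol does not expressly tie the re-calculation to that figure, and an SAP that is not shown may set its own target. The SD definition is an omission of a kind often left to an SAP, and the porcine source may settle it.

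Much of this is fair and limits the point. No patient numbers need to change. The effect on the re-calculation is an inference from the absence of any other target, not something the protocol states. The SD question would not be a finding on its own; it belongs here because correcting the error rate alone still leaves the power at 20 unreadable. Two-sided power is not at issue, since the protocol specifies a one-tailed test. The adequacy of 20 has been checked for one comparison at a time, not for osteotomy and stripping jointly.

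The objection does not remove the error. The figure is wrong as written, contradicts the number beside it, and is corrected nowhere else in the protocol. An SAP with a different target would conflict with the protocol as it stands.

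**Conclusion.** The concern holds. A Type II error rate of 0.80 is inconsistent with a sample of 20 under every standard variant of the calculation: it calls for 3 or 4 patients, or 3 per group if unpaired. Read as 80% power, the paragraph is coherent, with 19 required on the two readings closest to the stated figure and as few as 11 if 0.84 is in SDs of the within-patient difference.

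The trial is not underpowered for its stated one-sided effect. For a single comparison, 20 patients give at least 82% power on any reading with non-negative correlation. This rests on the protocol's 0.84 SD, a t-test, and correlations that are assumed here. The error should be fixed because it is the only power statement in the protocol and the only one available to the re-calculation at half enrolment.

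**What to change.** In section 11.0:

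1. Replace the Type II error rate of 0.80 with 0.20 and add that this is 80% power.
2. State in the same paragraph that the comparison is within-patient, and whether 0.84 is in SDs of the within-patient difference or in raw SDs. If raw, give the assumed correlation.
3. Give the one-sided power at 20 patients that matches that choice: 97.6% for difference SDs; 82.0%, 92.1% or 97.6% for raw SDs with correlation 0, 0.3 or 0.5.
4. State that the re-calculation at half enrolment uses the same Type II rate and SD definition.

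The cost is wording in one paragraph. The stated one-sided test needs no extra patients, and no study procedure changes.
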